Specific Aim 2: To evaluate the feasibility and preliminary effectiveness of a technology-delivered FBCO intervention for L/H families in rural Nebraska using RE-AIM and i-PARIHS. We will randomly assign participants to either the intervention or an enhanced standard care group (Figure 3). Sample Size Calculation. Sample size is based on the comparison of changes in BMI z-scores achieved by participants in FC-IVR with those achieved by participants in FC-workbook condition at 6 months post randomization²⁰. A total of 46 (23 per group) parent-child dyads achieves 80% power (alpha 0.05) to detect a significant difference between SC and IVR groups conditions. To account for a 25% attrition rate at 6-month we will recruit a total of 58 (29 per group) dyads. Participant Recruitment and Baseline Assessment Procedures. [name] will coordinate the recruitment of the participants with the help of CHWs. We will recruit a total of 58 dyads (Table 1). Baseline visits will take place at local community centers using private rooms. Dyads will complete informed consent, height, weight and waist circumference assessments, as well as complete a computer-based survey. Randomization will follow a random-numbers table (families/staff unblinded). Standard-Care. Families randomized to this group will receive FC-workbook. No additional materials or intervention contact will be provided. CHWs will follow a retention protocol to ensure these individuals return to 6-month assessments. Intervention Delivery. Families randomized to this group will receive the adapted version of the intervention described above. Drs. [name] and [name] will monitor IVR completion reports and assist the student-worker and CHWs in the on-going monitoring and engagement of participants during the intervention. Measurements and Data Collection. All measures (see table at PHS section for description) will be collected prior to intervention initiation and at 6 months post baseline (Figure 3). Weight will be assessed using a digital scale calibrated for accuracy prior to each assessment period using standard weights of a known quantity (e.g., 100-pound dumbbell). Height will be measured with a stadiometer, calibrated in 0.1-cm intervals. Waist circumference will be measured with a spring-loaded cloth tape measure at the level of the iliac crest using the average of the two closest measurements. Other Measures. Children and parents will complete measures of physical activity^{98,99}, eating behaviors¹⁰⁰, beverage intake¹⁰¹, quality of life^{102,103} acculturation^{104,105}, and health literacy¹⁰⁶. Parents will also complete home environment¹⁰⁷ surveys. During the 6-month assessment parents will complete program satisfaction surveys and a short exit interview with a CHW. Feasibility will be assessed according to intervention relevant factors (RE-AIM dimensions, engagement, attendance and completion rates), cost-effectiveness, cultural

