Maintenance	
 - Characteristics of completers vs non-completers - Intention to continue the intervention - Qualitative feedback on barriers/facilitators from participants/staff and leadership using i-PARIHS constructs 	
 -Demographic and clinical data from intake surveys [SW, CHWs] -Clinical data forms at 0,12 months [CHWs] -Qualitative interviews with participants, facilitators, staff, and health authorities [[name] , PI [name]] 	

Sample Size Calculation. Sample size is based on the comparison of changes in BMI z-scores achieved by participants in FC-IVR with those achieved by participants in FC-workbook condition at 6 and 12-month post randomization. A total of 46 (23 per group)

parent-child dyads achieves 80% power (alpha 0.05) to detect a significant difference between the FC-workbook and FC-IVR conditions, based on the relative BMI z-score differences (0.05) and standard deviation related to 6-month BMI z-score reduction for FC-IVR (0.06). To account for 25% attrition rate at 12-month, we will recruit a total of 58 (29 per group) parent-child dyads.

Cost Analysis: Costs will be assessed using time tracking spreadsheets and focused primarily on Aim 2 as it relates to the intervention delivery, though costs of participant recruitment will also be tracked using material and staff time to determine dollar amounts. [name] will complete A simple cost benefit analysis by assessing intervention implementation costs at 6-month post baseline by BMI z-scores reduction categories of unchanged, ≤ 0.1 , 0.1-0.25 and ≥ 0.25 , respectively.

Qualitative Analysis. Qualitative interviews will be recorded and transcribed in English or Spanish. The PI, with assistance from Drs. [name] and [name], will construct the interview codebook, with inductive codes added iteratively by in-depth reading of transcriptions until saturation is achieved. Transcripts will be double-coded in NVivo by [name]. Inter-coder reliability using Cohens kappa (goal > 0.80) will be assessed. The research team has extensive experience conducting qualitative investigation, possesses local linguistic expertise (Drs. [name] speak Spanish), and will be aided by community partners bilingual (English-Spanish) CHW staff.

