Health Departments (CDHD, ECDHD, TRPHD, CAPWN) will provide adequate space to allow for physical privacy when the participants discuss their informed consent and have

their risk assessments taken. All four Health Departments has an Automated External Defibrillator on site in the event of an emergent cardiac event. The PI ([name]) and at [name] will be at all for CWG in-person meetings and focus group, and the trained CHWs will present for participants in obtaining informed consent, conducting trainings for at home assessments. The PI and [name] are registered nurses, and the CHW are trained to provide first aid and emergency response action if needed. All investigators at each UNMC campus (Norfolk, Omaha) have password protected laptops, IT support, and private, locked office space. The principal investigator has two digital audio recorders. The grant will permit purchase of scales, stadiometers, iPads, and other equipment needed for baseline biomarker measures taken at the assessment points. A locked briefcase will be used to transfer hard copies of written study materials from the data collection site to the college.

Please see "Facilities and Other Resources" file from NIH proposal uploaded for more information.

LITERATURE REVIEW

34. References

Provide a full listing of the key references cited in the background (Section II.3). The references should clearly support the stated purpose of the study.

Please see "Bibliography and References" file from NIH proposal uploaded.

SECTION III

SUBMISSION DEADLINE

A. Full Board Review:

The IRB meets twice monthly, on the first and third Thursday of the month, with the exception of January and July when the IRB meets only on the third Thursday of the month. No more than 15 applications (e.g., initial review of a new study, re-review of a tabled study) will be reviewed at each meeting. All reviews are performed on a first-come first-served basis. The IRB meeting schedule and deadline dates can be found on the IRB website at www.unmc.edu/irb.

B. Expedited Review

Applications that qualify for expedited review have no submission deadline and can be reviewed independent of the IRB meeting schedule. Call the Office of Regulatory Affairs for assistance in determining if your study meets the requirements for expedited review.

ADDITIONAL REVIEW REQUIREMENTS

Final IRB approval and release of studies is contingent upon approval by the following UNMC committees or departments. Check the appropriate boxes:

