Including explore telemedicine and other ways to use new technologies that may facilitate evaluation of intervention outcomes. As well, coordinate with partners to provide all equipment necessary and rapidly deploy and restock PPE, including masks, gloves, goggles, gowns, hand sanitizer, and cleaning supplies. Proactively planning and updating protocols with contingency plans that could include altering procedures, cross-training staff, and expand the using available technology to replace in person contacts such as RedCap and Qualdrics. For example, for those having face-to-face interaction with participants maybe a more comprehensive PPE may be indicated, depending upon the context, prevalence of COVID-19 in the community, degree of contact with the client, and healthcare activity pursued at their home or non-home residential settings.

This collaborative approach for development of study protocols and routines are aimed not only for the participants safe completion of research activities but as well to assisting state and local health departments to balance the competing demands of their COVID-19 response. Following and contributing to standardize and endorse readiness protocol for CHWs responding to COVID-19. Furthermore, the majority of the contact with participants and all the in-person assessments will be completed by CHWs. Their engagement in the study will be assured via direct contract with the community partners as proposed by them and agreed before the proposal and ensured necessary resources at the funding budget (see letters of support). CHW are equipped, trained and supported as part of a well-functioning health system. Existing CHWs are well trained to prevent, detect and respond to COVID-19 as part of their regular work activities, including home visits for contact tracing, isolation and quarantine follow-ups.

As basic principle for protocols designed to ensure the physical safety and health of participants, follow DHHS and CDC guidance. For example, while performing any research activity CHW, CWG and all research personnel will be required to wear facemasks to

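### The 6-month height and weight behind the primary outcome are taken by unblinded staff from the group that recruits and engages families, with no masking and no repeat readings stated

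*Combined protocol and SAP*

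**What the plan says.** **Who measures.** Section IV (COVID-19), item 4 states that "the majority of the contact with participants and all the in-person assessments will be completed by CHWs". The Effectiveness row of Table 1 (Section 12.E) assigns the 0- and 6-month data to the student-worker and CHWs. Section 29.C has the investigators authorized to document consent take the screening measurements.

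**What the measurers know and do.** Section 12.B, Specific Aim 2: "Randomization will follow a random-numbers table (families/staff unblinded"); Section 12.C repeats this. Under Section 25.A, CHWs recruit from families they already serve. Under Intervention Delivery in Section 12.B, two investigators assist the student-worker and "CHWs in the on-going monitoring and engagement of participants during the intervention". CHWs also run the retention protocol for the standard-care (SC) arm. The 6-month assessment includes "a short exit interview with a CHW".

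**How measurements are taken.** Section 12.B specifies a calibrated digital scale and a stadiometer marked in 0.1 cm. Repeat readings are stated for waist only. Section 33 mentions CHWs "conducting trainings for at home assessments" without saying who takes those readings.

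**What the measurements feed.** The primary outcome in Section 12.B is the proportion of children reducing BMI z, tested by chi-square, with no minimum reduction stated. The sample size in Section 12.E rests on "relative BMI z-score differences (0.05") and "standard deviation related to 6-month BMI z-score reduction for FC-IVR (0.06").

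**The concern.** The people who take the readings know the arm and belong to the group that recruits families and helps to keep them engaged. Height depends on posture, head position, hair and rounding, and a reader who hopes for a good result can shift it without intending to. Calibration controls instrument error, not these.

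The trial is sensitive to this for two reasons. The target difference is only 0.05 z. And because any reduction counts as success, a small shift can move a child near zero change from one category to the other. If FC readings were shifted and SC readings were not, the shift would be part of the estimated effect.

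A softer form of the problem affects acceptability. CHWs help collect the satisfaction survey (Table 1) and conduct the exit interview, and both inform whether the programme goes on to further testing. Courtesy answers would flatter that evidence.

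**Working it through.** **Step 1. The plan's own figure.** Inputs from Section 12.E: difference 0.05, SD 0.06, and "achieves 80% power (alpha 0.05"), taken as two-sided.

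n per arm = 2 × (1.960 + 0.842)² × 0.06² / 0.05² = 2 × 7.85 × 1.44 = 22.6, so 23 per arm and 46 in total. This matches Section 12.E. (Section 4 prints a total of 56 beside the same 23 per group.)

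**Step 2. From centimetres to BMI z.** The documents give no conversion, so it is assumed. BMI is weight/height², so a height error e at height H changes log BMI by about −2e/H. With a slope k in z per unit of log BMI, the shift in z is k × 2e/H. Assumed: H = 135 cm, k = 2.5 to 4.5.

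| Over-read in FC only | k = 2.5 | k = 4.5 | Share of 0.05 |
|---|---|---|---|
| 0.10 cm | 0.004 | 0.007 | 7–13% |
| 0.25 cm | 0.009 | 0.017 | 19–33% |
| 0.50 cm | 0.019 | 0.033 | 37–67% |

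For example, 2.5 × 2 × 0.25/135 = 0.0093. Widening the assumptions to k = 2 to 6 and H = 120 to 150 cm gives 0.013 to 0.050 for a 0.5 cm error.

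**Step 3. From a shift in z to false positives on the stated primary test.** Assume normal changes with SD 0.06 in both arms, no true effect, SC mean change m between 0 and −0.03, and a spurious FC reduction b. The proportions reducing BMI z are Φ(−m/0.06) in SC and Φ((b − m)/0.06) in FC. With m = 0 and b = 0.010 these are Φ(0) = 50.0% and Φ(0.167) = 56.6%. With m = −0.03 and b = 0.030 they are Φ(0.5) = 69.1% and Φ(1.0) = 84.1%.

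The rejection rate comes from enumerating every pair of binomial counts at 23 per arm and applying the two-sided 5% chi-square test to each.

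| Shift b | Chi-square, uncorrected | With continuity correction |
|---|---|---|
| 0 | 5.0–5.4% | 2.4–2.6% |
| 0.010 | 7.1–7.8% | 3.6–4.1% |
| 0.015 | 9.6–10.8% | 5.1–6.1% |
| 0.030 | 22.8–26.7% | 13.1–17.7% |

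The ranges span the assumed SC mean changes.

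**Step 4. For comparison, a t-test on mean change.** The noncentrality is b / (0.06 × √(2/23)), with 44 degrees of freedom. The rejection rates are 8.6% for b = 0.010, 13.2% for 0.015 and 38.2% for 0.030. They describe a comparison of means, not the chi-square primary outcome.

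**The case against.** Five points can be made against this.

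- **Size.** A reader might infer that a small reading bias could produce much of the 0.05 effect. The figures do not support that: 0.25 cm gives a fifth to a third, and 0.1 cm, the stadiometer interval, gives 7 to 13%. Only about 0.5 cm, as an average shift in one arm alone, reaches 37 to 67%, and nothing in the documents shows that such a bias occurs. The calibrated digital scale makes misread weight less likely. This stands.
- **Same person.** A reader might also infer that each family is measured by its own CHW. No section says so; the overlap is between groups of staff. The other measurers named, the student-worker and the consenting investigators, are not described as masked either, so the gap remains.
- **Shared contact.** CHWs also follow the SC families, and most FC contacts are automated calls. Error common to both arms largely cancels. This limits the likely size but does not remove the route.
- **Home readings.** The Section 33 phrase does not say that families measure their own children, and Section IV describes staff cleaning the scale and stadiometer and removing protective equipment outside the home. It needs clarifying and is not evidence of family-taken outcomes. Waist tape readings do not enter BMI z at all.
- **Other documents.** A manual of procedures (Section 12.B) and an uploaded COVID protocol may say who measures whom. If so, the remedy is to bring that text into the protocol.

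That this is a feasibility study is a weaker defence. The plan powers the BMI z comparison, tests it at 0.05, and hypothesizes a significant difference in the proportion reducing BMI z.

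**Conclusion.** The concern holds as a gap in assessment procedure. The 6-month height and weight are taken by unblinded staff from a group that also recruits and engages families. The plan states no masking of arm or baseline values and no repeat height or weight readings.

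An FC-only over-read of 0.25 to 0.5 cm would shift BMI z by 0.009 to 0.033. On the stated chi-square test, shifts of 0.010 and 0.015 raise false positives from about 5% to 7–8% and 10–11%. A 0.030 shift, near the top of that range, gives 23–27%. Continuity correction lowers all of these.

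The sizes rest on the assumed height and slope, on normal changes with SD 0.06, and on a bias that is systematic and confined to one arm. The documents establish the opportunity for such bias, not its presence. This is a worthwhile, inexpensive improvement and not a flaw that invalidates the design. It has to be made before the 6-month visits, because differential error cannot be removed afterwards.

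**What to change.** Using existing staff, add to Section 12.B:

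1. At the 6-month visit, take height, weight and waist first, before the surveys and exit interview. Keep baseline values out of the measurer's sight, and ask families not to mention their programme.
2. Where scheduling allows, use a CHW or student-worker who has not engaged that family and is not told the arm. Record who measured and whether they knew the arm.
3. State that only staff readings on study equipment count for the primary outcome. Clarify the at-home wording in Section 33, and use any family-taken readings only in a sensitivity analysis.
4. Have the satisfaction survey self-completed out of the CHW's sight.
5. Reconcile Section IV item 4, Table 1 and Section 29.C on who takes the measurements.

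The cost is scheduling effort, with no change in sample size. Compulsory cross-site assessors or exit interviewers are not proposed: with four CHWs (Section 12.B) and four partner organisations (Section IV), they could mean regular travel. Masking will therefore be incomplete at any site with a single CHW, and this should be reported as a limitation.
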